# The association between loneliness and substance use Principal Investigator – [name]

## 1. PURPOSE OF STUDY

The proposed study will be the first to assess these cognitive, affective, and behavioral pathways by which loneliness impacts opioid use. Individuals with an opioid use disorder (OUD) reporting loneliness (N = 125) will be randomized to either a 6-session Cognitive-Behavioral Therapy for loneliness (CBT-L; n = 63) or a 6-session education control condition (n = 62), both delivered via telehealth. Telehealth delivery can be easily implemented and can increase reach and access to individuals not engaged in treatment. We will use an established brief CBT manual to address loneliness. We will assess loneliness, negative affect (i.e., depression and anxiety), and the quality and quantity of social interactions prior to, during, and after the intervention to evaluate the subsequent impact on opioid use trajectories. Participant will complete questionnaires pre-treatment, post-treatment, and at 1- and 2-months post-treatment. Given the need to elucidate mechanisms of opioid use and to test novel treatment approaches to reducing opioid use, we propose the following specific aims in this pilot study:

# Aim 1: To assess the efficacy of CBT-L's impact on loneliness, negative affect and the quality and quantity of social interactions among individuals with OUDs

Hypothesis: CBT-L will reduce loneliness and negative affect (i.e., depression and anxiety) and will increase the quality and quantity of social interactions compared to the education control.

# Aim 2: To assess the cognitive, affective, and behavioral mechanisms of the impact of CBT-L on opioid use trajectories

Hypothesis: CBT-L will reduce opioid use relative to the education control and these reductions will occur due to reduced loneliness, negative affect, and increased quality and quantity of social interactions.

# 2. BACKGROUND AND RATIONALE

Premature deaths from opioids have devastated U.S. communities, with nearly 50,000 opioid-related overdose deaths in 2017. The declining U.S. life expectancy has been largely attributed to opioid-related deaths. The multi-faceted public health response to this epidemic includes increasing access to evidence-based treatments, decreasing prescription opioid availability, and guidelines that promote non-pharmacological pain treatments. Understanding and addressing psychosocial stressors represents an essential area to reduce the demand for opioids. Through the use of adaptive coping strategies for psychosocial stressors, desire to use opioids might decrease thereby increasing engagement in social support.

Loneliness—a subjective emotional state characterized by the *perception* of social isolation—is a critical psychosocial stressor that can significantly impact opioid use. Loneliness is distinct from social isolation in that people with relatively few social contacts may not feel lonely, while individuals with rich social experiences may feel lonely. Loneliness impairs one's ability to effectively engage social support. Loneliness is evident across the lifespan and can be experienced by anyone, although it occurs at higher rates among those with psychiatric disorders, people who are objectively isolated, and people with chronic illnesses. A national study of

Page 1 of 20

adults ages 45+ found that over one-third reported loneliness and in 1,200 primary care patients, 20% reported being lonely. Loneliness can have deleterious effects on physical and mental health, increasing the risk for a constellation of chronic diseases and the development and exacerbation of psychiatric disorders and suicidal behavior. A meta-analysis of 70 studies found that loneliness increases odds of mortality by 29% in adjusted analyses accounting for the largest number of covariates.

Substance use is among the several unhealthy behaviors through which loneliness relates to increased premature mortality. Loneliness has been linked to tobacco and alcohol use in numerous studies,  including a national 10-year longitudinal study of over 3,000 people, where greater loneliness was associated with a 70% decreased likelihood of smoking cessation.  In cross-sectional data with 18-39 year olds, loneliness was associated with problematic drinking after accounting for depression, alcohol consumption, and coping style. 

Bohnert and Ilgen postulate that large-scale social factors (e.g., lack of employment opportunities, socioeconomic inequities) increase opioid use leading to depression and social isolation. The opioid epidemic further impacts communities through harmful effects on social networks and social cohesion emphasizing a need to increase meaningful social interactions. Opioid use can be reinforced through coping with social isolation that occurred as a result of finding social contact less rewarding and being concerned with the stigma attached to opioid use. Indeed, loneliness increases opioid use, is associated with a variety of negative consequences among individuals using opioids and is a critical factor that needs to be addressed in response to the opioid epidemic

Prevalence of loneliness among individuals with OUDs is very common. A study among a sample receiving methadone maintenance for OUD found that nearly three-fourths of women and over two-thirds of men reported moderate to severe loneliness. Prior studies among heroindependent individuals maintained on methadone found greater loneliness was associated with non-suicidal self-injury, sleep disturbance, greater pain intensity, and poorer quality of life key risk factors for relapse.  Loneliness and difficulty meeting abstinent friends is more commonly cited as a reason for craving among heroin users who relapse compared to those who remain abstinent. In a longitudinal study, the greatest reduction in heroin use was not just in people who were married, but those who reported a close personal relationship with his/her spouse. Accounts among individuals with an OUD indicate they often lack purpose largely driven by a sense of loneliness. Social isolation is both a motivation for heroin use and a risk factor for suicidal behavior among individuals addicted to heroin. 32-34 Addressing loneliness can affect treatment seeking. Those injecting drugs were 3 times less likely to seek OUD medications (e.g., methadone, buprenorphine) if they live alone. Additionally, treatment retention is associated with a perception of strong social support from one's family. A qualitative study revealed that there appears to be a subtype of people using heroin characterized as being more socially disconnected and these individuals have more cognitive barriers to engaging in methadone maintenance (e.g., harms of treatment outweigh the benefits) compared to other subtypes. Addressing loneliness in people using opioids can reduce risk factors for relapse or continued use and have a significant positive impact on how a person develops, maintains, and utilizes social support, including treatment seeking—all of which are essential factors in reducing opioid use.

To effectively reduce opioid use and related mortality, individual-level longitudinal data is needed to further understand the mechanisms by which loneliness impacts opioid use. The current proposal addresses this need by assessing hypothesized cognitive, affective, and

Page 2 of 20

behavioral mechanisms by which loneliness is associated with opioid use.

# 4. STUDY DESIGN

The proposed study will be the first to assess these cognitive, affective, and behavioral pathways by which loneliness impacts opioid use. Individuals with an OUD reporting loneliness (N = 125) will be randomized to either a 6-session Cognitive-Behavioral Therapy for loneliness (CBT-L; n = 63) or a 6-session education control condition (n = 62), both delivered via telehealth. We will assess loneliness, negative affect (i.e., depression and anxiety), and the quality and quantity of social interactions at baseline, during the intervention sessions, post-treatment, and at 1-month and 2-month follow-ups.

# 5. SUBJECT POPULATION

We will nationally recruit 125 adults with OUD for this randomized clinical trial. We estimate that our screen failure rate will be approximately 10-30%. We estimate attrition from the consent and baseline assessment to the end of the 2-month follow-up to be approximately 20%.

# *Inclusion of Vulnerable Populations:*

We will not purposefully recruit pregnant women, but neither will we exclude such participants from participating. The research activities are not expected to affect the pregnancy as it is a psychosocial intervention.

# 6. INCLUSION AND EXCLUSION CRITERIA

Inclusion criteria: To be eligible, participants must be ages 18+, understand English, have internet access, screen positive for an active OUD on the OUD Module of the Structured Clinical Interview for DSM-5 Research Version (SCID-5-RV), and screen positive for loneliness by scoring at least a T-score > 60 on the NIH Toolbox Loneliness Scale.

Exclusion criteria: Consistent with previously used telehealth-delivered assessments, we will exclude any participant who does not understand consent. Potential participants who are in the process of detoxifying as measured by the Subjective Opiate Withdrawal Scale will also be excluded.

## 7. RECRUITMENT METHODS

Participants will be recruited using Internet social media websites (e.g., Facebook, craigslist) and select print/web portals. Advertisements will target adults 18+ across the United States. Social media advertising (e.g., through Facebook, Reddit, Instagram) will be used to inform potential participants of the study and direct them to a University of Rochester landing page (see **Advertising** appendix) contact the project coordinators by phone or email for additional information. Paid searches will be used to potential participants through online keyword searches (e.g., opioids, alone) with a secondary tactic of finding people who are looking for

Page 3 of 20

paid research studies. Digital banner advertising will be used targeting individuals based on behaviors and search history. See **Phone screen script, information sheet, and verbal consent Appendix**.

## 8. CONSENT PROCESS

The consent document will be created using a REDCap-based electronic consent form. The IRB-approved consent form will be developed in REDCap, a secure, web-based, HIPAAcompliant, data collection platform with a user management system allowing project owners to grant and control varying levels of access to data collection instruments and data (e.g. read only, de-identified-only data views) for other users. We will contact UR IT support to create the REDCap eConsent. Potential subjects will participate in the consent process by eConsent obtained remotely with required remote consent process via Zoom (including toll-free phone option) or phone. **Verification with an Established Passcode:** In this approach, an agreed passcode is communicated via phone or email between the subject/subject's legally authorized representative and the study team. This passcode is saved as part of the subject's record for verification use later. The subject/subject's legally authorized representative at the time of accessing the survey/eConsent must then enter the passcode which is compared with the stored version entered by the study staff. eConsents accessed on personal electronic devices (e.g., computers, portable tablets, smart phones). During the remote consent process, research staff will thoroughly go over the consent form with the participant while clarifying any points as needed and answering all questions the subject may have. The informed consent form will contain a detailed description of the study procedures, along with statements regarding participants' rights to withdraw from the procedure at any time without consequences. It will be explained to participants in easy-to-understand language. The limits of confidentiality will also be explained, including the potential to break confidentiality in the acute risk of suicidal behavior or violence, or disclosures of unreported physical or sexual abuse of a child. This will occur prior to any data collection and the consent form will include text regarding the retention and use of that data.

Research staff ([name] or [name]) will sign their name at the bottom of the form to show that they have explained the research, answered all questions to the subject's satisfaction, that the subject has demonstrated comprehension of the information, and the participant will sign the eConsent. Subject signatures will be obtained using a typed signature. Once the consent form is signed and submitted, subjects will be able to receive a print-out of the paper copy, download a pdf, and/or receive an email with a PDF attachment of the signed consent form. Study procedures will continue once research staff receive the signed consent.

# Certificate of Confidentiality:

The Certificate of Confidentiality is automatically included as part of the notice of award.

With this Certificate, the investigators cannot be forced to disclose or use research information, documents, or samples that may identify the subject in any Federal, State, or local civil, criminal, administrative, legislative, other proceedings, or be used as evidence.

Page 4 of 20

Disclosure will be necessary, however, upon request of DHHS for audit or program evaluation purposes, or to other government agencies related to communicable diseases.

The investigator is not prevented from taking steps, including reporting to authorities, to prevent serious harm to yourself or others. The Certificate of Confidentiality will not be used to prevent disclosure to state or local authorities of child abuse and neglect, or serious harm to the subject or others.

## 9. STUDY PROCEDURES

Screening: The project coordinator will screen by phone following a script. Potential participants will provide verbal consent to complete the screening measures. Those individuals meeting eligibility who are interested in participating will be scheduled for a telehealth-based appointment to go over Consent, complete eConsent, and conduct a baseline assessment. Assessments and Intervention: Participants will be enrolled following consent and will complete the baseline assessment. Following the baseline assessment, participants will be randomized to condition (control or experimental) by a computer-generated algorithm. Participants will schedule a convenient time for their telehealth-based intervention sessions. Mid-treatment, posttreatment, and 30- and 60-day post-treatment follow-up assessments will also be conducted by telehealth. Participants will be paid \$40 each for the baseline and post-treatment assessment, \$20 for the mid-treatment assessment and \$30 each for the 30-day and 60-day follow-up assessments. Participants will also be paid \$20 for completing the first 3 sessions within 4 weeks. The posttreatment assessment will also include an exit interview for participants to describe acceptability of the intervention. All assessments and interventions will be conducted via Zoom (including toll-free phone option) or phone. If requested, participants will be sent a letter indicating study activities completed.

Randomization: We will randomize at the participant level using block randomization in groups of 4. All demographic and outcome variables will be assessed for baseline equivalency. Any between-group baseline differences will be controlled for statistically in all subsequent analyses with baseline differences being defined here as any absolute standardized mean difference (Cohen's d) greater than or equal to .15.

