Training for Research Staff: Drs. [name] and [name] will train the project coordinator to administer verbal consent and administer and score the assessment measures through instruction and extensive observed role play. [name] will model the administration of the consent and assessments while the coordinator observes, then they will observe the coordinator administer the consent script and baseline assessment instruments, providing feedback as needed. If more training is required, we will continue to model the interview and/or observe the interview until the coordinator reaches a satisfactory level of skill and comfort. The training will seek to promote reliable, fluid administration of the forms; maintaining a non-threatening, natural manner; accurately recording all responses; and careful checking to ensure that missing data is minimized. The same process will be used for each follow-up assessment session. The coordinator will be blinded to the participants' treatment conditions for the assessments.

Training for Interventionists and adherence rating: Interventionists with at least a master's degree in a counseling/health-related field and prior CBT training will deliver CBT-L and the education control. Drs. [name] and [name] will train the interventionists using the manual. Initial training will consist of lecture and role play "rehearsal" techniques. Ongoing supervision will also be provided throughout the study. No identifying information will be used, noted, or discussed during supervision.

Because each CBT-L session has unique content, we developed session adherence measures that itemize the session-specific content (See **Adherence Checklist Appendix**). Each session will emphasize the completion of worksheets for identifying/changing maladaptive thoughts. Adherence scores will be given for each session and the entire intervention by transforming the total number of points into a percentage of content delivered. Study therapists will track adherence as they complete sessions.

Supervision for Research Team and Interventionists: Weekly meetings will be conducted to focus on monitoring: a) recruitment, b) conducting interviews, c) coding interview data, d) communication between research staff, e) retention; f) completeness of documentation, and g) storing and safeguarding data. To maintain blinding, separate meetings among interventionists and coordinator will occur as needed.

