Exit Interview. The exit interview will assess overall impressions and impact of treatment, relationship with the therapist, and ways to improve the treatment (See Appendix). The exit interview will inform future feasibility and acceptability and to further refine the intervention protocol as needed. A modified version of the Abbreviated Acceptability Rating Profile will be used to further assess treatment acceptability.

Perceives Invalidation of Emotion. The Perceived Invalidation of Emotion Scale (PIES) is a 10-item measure assessing the extent to which the respondent perceives that an individual implies that their emotions are incorrect or inappropriate. Research supports the psychometric properties of the measure and construct. 90 The PIES will be administered at the baseline and post-treatment assessments.

Attachment The Revised Adult Attachment Scale-Close Relationship version (AAS) assesses 3 dimensions of adult attachment (close, dependent, anxiety) over 18 items on a 5-point Likert scale (1 – Not at all characteristics of me to 5 – Very characteristic of me). The scale is widely used with strong psychometric properties.91 The AAS will be delivered at baseline and post-treatment assessments.

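### As the available text reads, the blinded coordinator gives a post-treatment assessment that includes an exit interview about the treatment, with the 30- and 60-day outcomes still to collect

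*Combined protocol and SAP*

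**What the plan says.** Under Training for Research Staff in section 9, senior staff will "train the project coordinator to administer verbal consent and administer and score the assessment measures". Follow-ups are included: "The same process will be used for each follow-up assessment session". The paragraph ends with the blinding commitment, "The coordinator will be blinded to the participants' treatment conditions for the assessments", and exempts no visit.

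Under Assessments and Intervention, section 9 gives the schedule after randomisation: "Mid-treatment, posttreatment, and 30- and 60-day post-treatment follow-up assessments will also be conducted by telehealth". It then adds to the post-treatment visit: "The posttreatment assessment will also include an exit interview for participants to describe acceptability of the intervention".

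The Exit Interview entry under Measures gives the content: "The exit interview will assess overall impressions and impact of treatment, relationship with the therapist, and ways to improve the treatment". It also adds a rating: "A modified version of the Abbreviated Acceptability Rating Profile will be used to further assess treatment acceptability".

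One safeguard for the blind is stated, under Supervision for Research Team and Interventionists: "To maintain blinding, separate meetings among interventionists and coordinator will occur as needed".

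**The concern.** The plan promises a blinded assessor, and its own schedule includes a conversation about the treatment while outcome collection is still under way. The two arms are easy to tell apart by content. CBT-L works on maladaptive thoughts and behavioural activation; the control teaches diet, water intake, exercise and sleep. A participant asked how the treatment could be improved would probably name something that identifies the arm.

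At stake is detection bias in outcomes collected through an interviewer after that conversation. The Timeline Follow Back is taken at every time point and is the secondary outcome in Table 1. The SCID-5-RV opioid module is repeated at the final follow-up and is listed as tertiary/exploratory. Neither has an independent check: Measures explains that urine screens would be hard to obtain without in-person contact, and section 10 rules out audio recording, so a blinded second rating from recordings is not possible.

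**Working it through.** The plan gives no figure to reproduce. The check sets the passages side by side and counts the exposed visits.

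1. **Who assesses.** Training for Research Staff in section 9 gives administration and scoring to the project coordinator and extends the training to each follow-up session. No other outcome assessor is named for these visits in the available text.
2. **What the post-treatment visit contains.** Section 9 makes the exit interview part of that assessment. Read with step 1, the coordinator would conduct it. This is an inference; no sentence assigns the interview to the coordinator.
3. **What the answers could reveal.** Open remarks on session content probably reveal the arm. Answers on the therapist need not, because one pool of interventionists delivers both conditions and each participant keeps the same therapist for all six sessions. Nothing available shows that the acceptability rating discloses the arm.
4. **Whether the stated safeguard covers this.** Separate meetings limit what interventionists tell the coordinator. They do not limit what a participant says. Weekly meetings also cover the conduct of interviews and the coding of interview data. If that includes exit interviews, answers could reach the coordinator even when someone else conducts them.
5. **How many visits are exposed, if the coordinator hears the interview.** Assessments after randomisation (sections 9 and 14): mid-treatment, post-treatment, 30-day, 60-day = 4.
   - Interview after the post-treatment measures: 30-day and 60-day, so 2 of 4.
   - Interview before them: post-treatment is added, so 3 of 4. The available text gives no order within the visit.
6. **How many participants.** Section 5 expects about 20% attrition from consent and baseline to the end of the 2-month follow-up: 125 × (1 − 0.20) = 100 expected at the 60-day visit.

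Steps 5 and 6 count exposure only. The documents give nothing from which to estimate how far a coordinator's knowledge of the arm would shift the recorded outcomes.

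**The case against.** The strongest objection is that the gap cannot be established. Part of the text between the Exit Interview entry and section 10 was not available to this review, nor was the appendix to which that entry refers. Either may name the interviewer. Section 16, on privacy, speaks of trained research interviewers in the plural, and the exit interview is not a line in Table 1. This objection stands, and it makes the point conditional.

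A reader might infer something stronger: that the plan unblinds its assessor, or that the trial's results are therefore biased. The documents do not support either reading. No passage assigns the interview to the coordinator, and the primary outcome is a participant-rated scale.

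Three further points also stand. First, the exit interview is not the only route to disclosure: Treatment utilization is asked at follow-up, with CBT among its examples, and participants may mention their sessions at any visit. Second, the Timeline Follow Back is itself a participant report, and nothing makes participants blind to session content, so their own reporting bias remains whoever interviews them. Third, the stakes are limited: section 1 calls this a pilot and section 17 calls the mediation analysis exploratory.

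These points reduce the weight of the concern without removing it. The plan chose to blind its assessor, and the exit interview is a scheduled discussion of the treatment itself. Section 12 also expects the data to guide a larger trial.

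**Conclusion.** The point holds in conditional form. Followed as the available text reads, the schedule works against the plan's own blinding rule, and the one stated safeguard does not reach the problem. If the coordinator hears the exit interview, the blind is probably lost for 2 of the 4 post-randomisation assessments, or 3 of 4 if the interview comes first. This affects mainly the later Timeline Follow Back and the final SCID-5-RV module. The UCLA primary outcome is less exposed, though the coordinator still administers and scores it by Zoom or phone.

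This rests on two assumptions: that the coordinator conducts the interview or learns its content, and that open answers reveal the arm. The first is inferred from section 9 and could be overturned by the unavailable text. The finding is a gap in how the blind is protected, with low to moderate stakes. It is not proven unblinding, and no size of bias can be stated.

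**What to change.** In section 9, under Assessments and Intervention and in the Exit Interview entry, state three things:

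- **Order.** The exit interview and acceptability rating come after all post-treatment outcome measures.
- **Who.** They are either self-completed on a restricted-access form, or conducted by an existing team member who collects no outcomes from that participant and did not treat them.
- **Access.** The answers stay hidden from the coordinator, including in weekly meetings, until that participant's 60-day outcomes are entered.

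If the unavailable text already names a separate interviewer, only the order and the access rule are needed.

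The cost is low. A form needs protocol wording and restricted access; section 8 describes REDCap for eConsent only, so the form would have to be set up. Written answers are less rich, which matters because the interview is meant to help refine the intervention, and a form departs from the Zoom or phone format that section 9 sets for all assessments. The oral option keeps the richer answers but needs some scheduling and a suitable team member, whose availability the documents do not show. Keeping the interview at post-treatment avoids losing acceptability data to later dropout. The change does not close other disclosure routes, such as the treatment-utilization questions.
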